Data will be maintained by NJH with permission of the Departments of Health in each state, who consider the COVID-19 related survey questions to be part of quitline care (i.e., not requiring informed consent). The HH4 team will analyze de-identified aggregated state quitline data provided by NJH. With quitline data, investigators will explore the impact of coronavirus on individuals' *risk perception, change in motivation to quit, change in tobacco use, and engagement in treatment resources*, as well as explore 6-month quit rates during the pandemic as compared to 1 year earlier, adjusting for any imbalance in caller characteristics.

Measures

Intervention Effectiveness: Smoking Cessation

1° Outcome measure: Verified 7-day point prevalence tobacco abstinence at 6-month follow-up

The proposed measure is self-reported abstinence from all tobacco products (including electronic cigarettes) for the past 7 days, confirmed by a saliva cotinine of ≤ 10 ng/ml or CO <9 ppm, which are consensus values.^{96,97} We will obtain saliva samples by mail, an accepted method.⁹⁸ Our definition of tobacco abstinence does not allow for e-cigarette use because the FDA has deemed e-cigarettes to be tobacco products⁹⁹, but it allows for NRT use, as recommended.⁹⁶ Because of uncertainty about the risk/benefit of e-cigarettes for cessation, we will calculate a secondary tobacco abstinence measure that allows for use of e-cigarettes but no other tobacco products. (In the HH2 trial, the alternative calculation produced very small differences in abstinence rates that

did not change study results.) Because NRT use produces a false positive cotinine, the biochemical validation criterion for a patient reporting NRT use at 6 months will be an expired-air carbon monoxide measurement of <9 ppm, obtained at an in-person visit.¹⁰⁰ Subjects who self-report smoking, do not provide a saliva sample or CO measurement, whose cotinine or CO measures exceed the cut-offs, or who are lost to follow-up at 6 months will be counted as smokers.^{96,97,100} Obtaining saliva samples in low-contact intervention trials, including recent studies in hospitalized smokers, is challenging.^{55,101} We will offer a \$150 incentive uploaded to their payment card for return of a sample, which produced a 69% return rate in HH2 (with no difference by study arm).

2^o Outcome measures of tobacco use: to be calculated using standard definitions.⁹⁶

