- *Depressive symptoms: 8-item Center for Epidemiologic Studies Depression Scale¹⁰⁴ at baseline and follow-up. Rationale: depression is common in smokers,¹⁰⁵ depressive symptoms predict post-discharge relapse.¹⁰⁶
- *Alcohol use: AUDIT-C,¹⁰⁷ a 3-item survey assessing frequency, quantity, and binge drinking. Rationale: heavy alcohol use is associated with difficulty quitting.
- *Other substance use: Any past month use. Rationale: other substance use is common in smokers and may be associated with lower quit rates after treatment.

Implementation and Process Measures. Data at each site will be collected to monitor rates of study eligibility, refusal, intervention delivery, and follow-up completion, using the following RE-AIM model constructs.¹⁰⁸ Reach: % of identified smokers admitted during the study who are seen by a TTS counselor, are eligible for the study, and enroll. Effectiveness: the 1^o trial outcome. Implementation: % of subjects assigned to each study arm who receive relevant components (See Table 3). These data will be obtained from TelASK, NJH, and SmokefreeTXT internal monitoring systems as well as from the EHR.

Statistical methods

Sample Size

A total sample of 1350 (675/group) will have 84% power to detect a 6.5% absolute difference in primary outcome, verified 7-day point-prevalence abstinence at 6 months, assuming rates of 16.5% (eReferral group) and 23% (PTCM group), and a 2-tailed type I error rate of .05. The rate ratio (1.39 = .23/.165) is clinically meaningful and resembles the ratio found in the Cochrane meta-analysis of smoking cessation interventions for hospitalized patients.² **Rationale:** eReferral: We conservatively estimate the abstinence rate from the HH trial (17% and 16%)⁵⁶; patients in both conditions were referred to a quitline. PTCM: Intervention resembles that of HH1 (25% abstinence rate);³⁹ we conservatively estimate 23%.

VII. RISKS AND DISCOMFORTS

The potential risks to subjects include potential psychological distress from speaking with a counselor or answering questions about their smoking, and a loss of confidentiality of their healthcare data. In addition,

those patients who are randomly assigned to receive a free supply of FDA-approved smoking cessation medication may be subject to the potential side effects of using nicotine replacement therapy (NRT).

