Data quality (including visits completed during intervention window, missing data, and recruitment rates) will be monitored monthly by the database manager, [name], and systemic data problems will be reported to the PI. IVR calls, emails, and text messages provided by TelASK, Inc. will be monitored for quality assurance. In addition, the Project Manager will review 10% of the counseling progress notes for adherence to the protocol. Outcomes data will be analyzed by [name], a biostatistician, using logistic regression and survival analysis. The alpha level will be set at 5%. Interim data analysis will be conducted halfway through the trial and results will be reported in the annual NIH progress report.

The principal investigator, [name], and the Project manager will be responsible for monitoring the safety and effectiveness of this trial, executing the data safety and monitoring (DSM) plan, and complying with reporting requirements. [name] will supply a summary of the DSM report to the NIH on an annual basis as part of the progress report.

Safety Monitoring Plan: The main risks to participation in the study include the potential for psychological discomfort during counseling sessions and side effects to the FDA-approved medications. We will protect against risks of psychological discomfort by using language that is meant to offer assistance and promote health, rather than demonstrate blame or guilt. In order to protect against risk from pharmacotherapy usage, these steps will be taken:

(1) Medication is being provided only to patients in the PTCM intervention arm. These participants also receive automated telephone calls by IVR 7 times in the 3 months after hospital discharge, especially soon after discharge (at 3 days and 2, 4, 6, 8, 10, and 12 weeks). At each call, patients are specifically asked about any side effects or problems. Those who report them are advised to speak to a live tobacco counselor. Patients who request a medication refill after the initial 30 day supply are required to speak to a live counselor, who asks about medical problems before authorizing a refill of medication. Study staff will be required to report any unexpected or questionable reports of adverse effects to the study PI ([name]). These will be reviewed at the weekly study staff meeting. If more urgent, the PI will review immediately.

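### Does the loosely described halfway interim analysis push the type I error above the planned 5%?

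*Combined protocol and SAP*

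**What the plan says.** The Data Monitoring Plan in section IX assigns the outcomes analysis to a biostatistician using logistic regression and survival analysis. It then says: "The alpha level will be set at 5%. Interim data analysis will be conducted halfway through the trial", and adds that "results will be reported in the annual NIH progress report". The next paragraph says that the principal investigator and "the Project manager will be responsible for monitoring the safety and effectiveness of this trial".

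Two places in section VI bear on this. The Sample Size paragraph plans 1350 participants (675 per group) for 84% power at 16.5% versus 23%, "and a 2-tailed type I error rate of .05", and does not mention an interim. Implementation and Process Measures, which lists RE-AIM constructs, has the entry "Effectiveness: the 1^o trial outcome".

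The primary outcome is verified 7-day abstinence at 6 months. The Measures subsection counts as smokers: "Subjects who self-report smoking, do not provide a saliva sample or CO measurement, whose cotinine or CO measures exceed the cut-offs", together with those lost to follow-up.

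**The concern.** The interim sentence comes straight after the outcomes-analysis and alpha sentences, while data-quality monitoring is described separately as a monthly task. The natural reading is therefore that the look covers outcomes data. The endpoint, the meaning of halfway, the decision that could follow, the boundary and the access rule are all missing.

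Two harms could follow.

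- **Error rate.** If the interim could establish efficacy at 5% and the final test could do so again, the real error would exceed the stated 5%.
- **Conduct.** If the team running an unblinded trial saw abstinence by arm midway, its effort in obtaining saliva or CO samples could become uneven. An unreturned sample counts as smoking, so uneven effort could move the primary outcome even though self-report is verified.

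**Working it through.** **1. Reproduce the planned power.** Inputs (Sample Size, section VI): 675 per group, 16.5% and 23%, two-sided 0.05.

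- Mean rate (0.165 + 0.23)/2 = 0.1975.
- Null SE = sqrt(2 × 0.1975 × 0.8025/675) = 0.02167.
- Alternative SE = sqrt((0.165 × 0.835 + 0.23 × 0.77)/675) = 0.02160.
- Power = Φ((0.065 − 1.96 × 0.02167)/0.02160) = Φ(1.04) = 85.2%.
- With continuity correction, subtract 1/675 from the difference: 83.5%.

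The stated 84% lies between these, so it is the power of a single test with the whole 0.05.

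**2. Error if both looks could decide.** For two looks at |Z| > 1.96, with correlation sqrt(t) between them at information fraction t:

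overall error = 1 − P(|Z1| < 1.96 and |Z2| < 1.96).

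| t (assumed) | overall two-sided error |
|---|---|
| 0.25 | 9.1% |
| 0.3 | 8.9% |
| 1/3 | 8.8% |
| 0.4 | 8.6% |
| 0.5 | 8.3% |
| 0.6 | 8.0% |

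A simulation of 2,000,000 binomial trials (337, then 675 per arm, both rates 16.5%) gave 8.33% for either look, 4.99% for the interim alone and 5.04% for the final test alone.

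The document does not define halfway, so t is an assumption. If it means half enrolled, with even enrolment over M months and a 6-month outcome, then t = (M/2 − 6)/M. That is 6/24 = 0.25 for an assumed 24 months and 12/36 = 0.33 for an assumed 36 months.

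**3. Error if only the final test decides.** The error is P(|Z2| > 1.96) = 5.0%, whatever was tabulated earlier. The difference at t = 0.5, 8.3 − 5.0 = 3.3 points, consists entirely of trials that cross at the interim and not at the end. They become false positives only if the interim can end the trial for efficacy or support a claim. A futility stop cannot add to the error, since rejection would then be possible only at the end.

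**4. Which case the text describes.** The 8.3% needs three things: verified abstinence as the interim endpoint, a comparison of arms at 5%, and an efficacy decision. The text states none of them. It gives one use, a progress report to the funder.

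**5. What a boundary would cost.** O'Brien-Fleming-type spending at t = 0.5 gives |Z| > 2.963 at the interim and 1.969 at the end. With drift 0.065/0.02160 = 3.01, power is 85.2%, against 85.3% for a single look on the same calculation. The cost is trivial, but the boundary would govern a decision that the plan does not contain.

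**6. Size of the conduct concern.** HH2 (Preliminary Work) had self-reported 6-month abstinence of 31% and 27%, and verified abstinence of 17% and 16%. Measures reports a 69% sample return with the same $150 incentive. Assume a 5-point gap in return between arms.

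- If every extra sample confirmed abstinence, the shift would be 0.05 × 0.27 = 1.4 to 0.05 × 0.31 = 1.6 points.
- If 69% applies to self-reported quitters, the share of returned samples confirming abstinence was 0.17/(0.31 × 0.69) = 79% and 0.16/(0.27 × 0.69) = 86%. The shift is then about 1.2 points in either case (0.05 × 0.31 × 0.79, or 0.05 × 0.27 × 0.86).

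The planned difference is 6.5 points. The 5-point gap is itself only an assumption, because Measures says that HH2's return did not differ between arms.

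**The case for a change.** The strongest argument for a change is that a reporting route is not a decision rule. Nothing in the document rules out acting on a striking interim result, so a reader of the final p-value cannot tell from the plan alone whether 5% or 8 to 9% applies. No independent monitor is named, those responsible for the trial also monitor its effectiveness, and one sentence would settle the matter at no cost in power.

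Part of this stands. The look is under-described, and the arithmetic for the unfavourable case is right. A clarifying sentence would do no harm.

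The rest is weaker. Silence about stopping is not permission to stop, and a design whose power uses the whole 0.05 once is most simply read as having one decisive test. The access argument joins a RE-AIM label in a list of process measures to a general statement of responsibility, although the outcomes analysis is assigned to a biostatistician. The website on which staff see results in real time belongs to the outreach vendor; the 6-month outcomes come from REDCap surveys, study staff and mail.

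The available remedies also go further than clarification. Restricting the look to pooled data would withdraw a comparison by arm whose intent is unknown. The version is dated July 30, 2020, and the document does not show whether halfway has already passed; if it has, prospective wording would change nothing.

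**Conclusion.** No change to the plan is needed. The interim analysis is described too briefly, but the gap is one that analysts fill sensibly: the look is reported to NIH, and the primary comparison is made once, at the end, at two-sided 0.05. On that reading the type I error is 5.0% and the planned power stands.

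The figure of about 8.3% (8.0% to 9.1% for information fractions from 0.6 down to 0.25) is correct only under three conditions that the plan does not state: verified abstinence is the interim endpoint, arms are compared at an unadjusted 5%, and the result can support an efficacy claim or an efficacy stop. The conduct concern amounts to roughly 1.2 to 1.6 points under an assumed 5-point gap in sample return, and the only return figure in the document shows no difference between arms.

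The conclusion rests on the absence of any early claim or stop in the document. If the trial were in fact stopped or declared positive at the interim, the 8.3% calculation would apply. The final report would then need to say what was examined, by whom and at what level.

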Post-discharge outreach Modality Frequency	Phone call 1 time	Automated contacts within 3 months after discharge (welcome at discharge, 3d, 2, 4, 6, 8, 10, 12wks). Contact modalities: automated IVR call, followed by automated email/text message.
Free Counseling Services offered When offered Provider, location	5-call QL protocol (3 mo) At initial quitline call Tobacco coach (based at NJH)	Tobacco coach (based at hospital) offered at 7 automated contacts through IVR call//email/
Free Medication Type When provided	NRT x 4 wks Mailed by QL after discharge	NRT x 8 wks Given at discharge
Care coordination	Feedback reports sent QL→EHR (no dedicated coordinator)	Tobacco coach interfaces with PCP team via EHR messages; if EHR not available (outside hospital)

		system), then communicate via faxed notes
EHR integration	Yes (link to QL)	Yes (via Coach)
Patient choice	n/a	IVR call followed by email/text message (patient's choice)

QL=quitline, NJH=National Jewish Health quitline, EHR = electronic health record, IVR = interactive voice response, PCP = primary care provider, SmokefreeTXT = free NCI text messaging program

Interventions

1. Personalized Tobacco Care Management (PTCM). Adding to the components of the Sustained Care Model, PTCM will incorporate a tobacco coach based at each hospital to coordinate care with the patient and gradually transition care to the patient's outpatient primary health care team. There are three main components to the intervention:

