- **Proactive Automated Contacts (IVR Phone, Email and/or Text Message):** PTCM aims to enhance patient engagement by adding the option of email and text messaging to the outreach done by IVR calls in HH1 and HH2 trials. An automated communication platform will generate 7 personalized, automated outbound contacts to smokers by IVR followed by their choice of email and/or text message for 3 months post-discharge (at 3 days and 2, 4, 6, 8, 10, and 12 weeks). TelASK Technologies (Ottawa, Canada), our technical partner, developed and implemented the IVR platform successfully in the HH1 and HH2 trials. Each IVR call/email/text will assess: (1) current smoking status and intention to quit, (2) current smoking cessation medication use, and (3) medication side effects. At each contact patients will have the option to request additional support from the tobacco coach; separately, some responses will trigger a call back from the coach. Criteria to trigger a live counseling call will be: (1) patient's request; (2) patients who resumed smoking after discharge but still want to quit; (3) patients who stopped using pharmacotherapy before the end of an 8-week course; (4) patients reporting medication side effects.

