2. **eReferral**, the second intervention, is a new technologically-advanced, automated strategy that links hospital EHRs to a quitline via a bi-directional connection¹¹ using Direct, a national encryption standard for securely exchanging clinical healthcare data (**Figure 3**). Quitlines offer free cessation support (counseling and often an NRT sample) to U.S. smokers who call a toll-free number.^{13,14} Proactive telephone counseling is an efficacious smoking cessation treatment method that incorporates motivational interviewing, cognitive-behavioral counseling, and relapse prevention strategies, usually in a multi-session call format.^{9,91,92} For the study, the RA enrolling the patient will make the eReferral from the EHR at discharge. Quitline staff will then attempt to contact the smoker by phone within 72 hours to offer the standard services offered by the state quitline (multiple-call counseling protocol and 4 weeks NRT).^{12,73} Up to 3 contact attempts are made but in practice successful connection may take several weeks. A report of the quitline referral is sent securely to the EHR where the patients’ primary health care team can access it and act upon it as needed. In accordance with best practices for Federal Health IT as determined by the Office of the National Coordinator for Health Information Technology, eReferral employs standardized recommendations for message structure, content, transport, and delivery to maximize interoperability. The standardized data elements facilitate quality improvement and reporting metrics for NHQM. The quitline provider for this study, National Jewish Health (NJH), currently serves all MA and PA patients under state contract⁹³ and will also serve Vanderbilt study participants to ensure uniformity of eReferral across sites.

VI. BIOSTATISTICAL ANALYSIS

Data Collection

Baseline data: Each site’s RA will do a baseline survey after enrollment and collect contact information for the patient and up to 3 close contacts in order to minimize loss to follow-up. To minimize burden on hospitalized subjects, some data will be obtained from hospital records and the standardized data collection

Figure 3: eReferral Process

form used by smoking counselors who provide inpatient counseling at each site. Smoking counselors and RAs will be trained to ensure that they complete data forms consistently across all sites.

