(2) The study PI ([name]) will review provide back up to study staff for all medical questions that arise during participant enrollment or study progress.

(3) The study PI ([name]) will review any serious adverse events and report them appropriately to the IRB. SAEs that represent hospital readmissions are anticipated to be frequent in this population of patients with medical illness. Each will be reviewed by the study PI to ensure that the readmission is not related to study medication.

Adverse Events Reporting: Participants who report any adverse events to the smoking counselor will be advised to discuss these side effects with their doctor. The reports of the adverse events will be summarized and reviewed by the PI on a monthly basis and reported to the IRB upon renewal of approval and to the funding agency upon continuing review. Serious adverse events will be reported immediately to the PI who will contact the participant, the participant's physician and the IRB.

X. REFERENCES

1. U.S. Department of Health and Human Services. *

The health consequences of Smoking—50 years of progress: A report of the surgeon general.* . Atlanta (GA): Centers for Disease Control and Prevention, National Center for Chronic Disease Prevention and Health Promotion (US) Office on Smoking and Health; 2014. <http://www.surgeongeneral.gov/library/reports/50-years-of-progress/index.html>. Accessed 11/25/15. NBK179276 [bookaccession].
2. [name] NA, Clair C, Munafo MR, Stead LF. Interventions for smoking cessation in hospitalised patients. *Cochrane Database Syst Rev.* 2012;5:001837.
3. [name] NA, Munafo MR, Stead LF. Smoking cessation interventions for hospitalized smokers: A systematic review. *Arch Intern Med.* 2008;168(18):1950-1960.
4. Centers for Disease Control and Prevention (CDC). Cigarette smoking among adults and trends in smoking cessation - united states, 2008. *MMWR Morb Mortal Wkly Rep.* 2009;58(44):1227-1232.

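### Non-serious medication side effects are actively sought only in PTCM, although eReferral participants are also offered NRT, so non-serious event counts could not be compared between arms

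*Combined protocol and SAP*

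**What the plan says.** **PTCM.** Section V (Interventions, Proactive Automated Contacts) lists what each automated contact assesses, including "2) current smoking cessation medication use, and (3) medication side effects". Its criteria for a live call from the coach include "4) patients reporting medication side effects". Section IX (Safety Monitoring Plan, step 1) adds "These participants also receive automated telephone calls by IVR 7 times in the 3 months after hospital discharge" and "At each call, patients are specifically asked about any side effects or problems".

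**eReferral.** Table 2 gives the free medication in this arm as "NRT x 4 wks Mailed by QL after discharge". The eReferral description in Section V gives the quitline's standard services as "multiple-call counseling protocol and 4 weeks NRT". The information it describes as coming back is limited: "A report of the quitline referral is sent securely to the EHR". Table 3 adds quitline data on reach, NRT sent or received, counseling enrolment and calls completed.

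**Both arms.** Section IX (Adverse Events Reporting) concerns events that participants report to a smoking counselor, without naming an arm: "The reports of the adverse events will be summarized and reviewed by the PI on a monthly basis". The summary then goes to the IRB and the funder. The section does not say that it is split or compared by arm. Step 1 of the Safety Monitoring Plan opens by stating that medication is supplied in the PTCM arm alone.

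**The concern.** Both arms are offered nicotine replacement, but the described system for finding its non-serious side effects covers one of them. A patch rash in a PTCM participant is prompted for repeatedly, and a positive answer triggers a call from the coach. The same rash in an eReferral participant reaches the study only if the participant volunteers it and someone passes it on, and no such path from the quitline is described.

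Two things are at stake. First, any statement about tolerability by arm would rest on unequal ascertainment, in a trial that compares two ways of delivering the same drug class. Second, a non-serious problem with mailed NRT could go unnoticed. The stated reason for monitoring only PTCM is contradicted elsewhere in the protocol, so the asymmetry looks more like an oversight than a considered choice.

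**Working it through.** **1. The plan's own figure.** The listed contact times are 3 days (1) and weeks 2, 4, 6, 8, 10 and 12 (6): 1 + 6 = 7, which agrees with the stated 7. The welcome contact at discharge in Table 2 is not counted. Seven is the scheduled maximum. In the first Helping HAND trial a median of 4 of 5 calls was completed; carried over as a rough guide, 7 × 4/5 = 5.6.

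**2. Scheduled ascertainment, arm against arm.**

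| Question | PTCM | eReferral |
|---|---|---|
| Medication side effects | up to 7 | none described |
| Hospital admissions (1, 3, 6 months) | 3 | 3 |
| Deaths (proxies, hospital records, National Death Index if needed) | yes | yes |
| Planned free NRT (Table 2) | 8 weeks | 4 weeks |

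The second and third rows come from Section VI (Health and health care utilization outcomes), which makes no distinction by arm. Section IX treats readmissions as serious events reviewed by the PI. The gap therefore concerns non-serious events.

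**3. Do the common surveys close the gap?** The measures in Section VI cover abstinence, treatment use, admissions, depressive symptoms, alcohol and other substance use. No medication side-effect item is listed. The questionnaires themselves are not in the documents.

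**4. Size, as an illustration only.** The documents give no adverse event rate and no capture rate. Assume the same true proportion with a non-serious side effect in both arms (10% to 30%), 60% to 95% capture when asked, and 10% to 30% capture when not asked. Expected recorded participants = 675 × true proportion × capture:

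| True proportion | PTCM, 60% | PTCM, 95% | eReferral, 10% | eReferral, 30% |
|---|---|---|---|---|
| 10% | 40.5 | 64.1 | 6.8 | 20.3 |
| 30% | 121.5 | 192.4 | 20.3 | 60.8 |

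The true proportion cancels in the ratio. Smallest: 0.60/0.30 = 2.0. Largest: 0.95/0.10 = 9.5. If nothing is captured without asking, eReferral shows zero and the ratio is undefined. The direction needs only that asking captures more than not asking.

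**5. Why the bias cannot be removed afterwards.** Observed ratio = true ratio × (PTCM capture / eReferral capture). An observed ratio of 4 fits a true ratio of 1 with a capture ratio of 4, or a true ratio of 2 with a capture ratio of 2. With 8 against 4 weeks of planned supply a true ratio above 1 is plausible, and nothing in the plan estimates the capture ratio.

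**The case against.** The strongest reply is that the plan makes no comparison of adverse events between arms. Its outcomes are abstinence, engagement, utilization, mortality and process measures, and the monthly review exists to protect participants. That is correct. The bias appears only if counts are tabulated by arm, and no such table is specified. The reply does not meet the other half of the point: for protection too, non-serious side effects are sought in only one of two arms offered NRT.

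A reader might go further and infer that eReferral participants are never asked about side effects, that the summary will show nothing for that arm, and that an excess in PTCM is certain. The documents do not support this:

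- Admissions and deaths have a common route in both arms, so a side effect that leads to admission can be found in either.
- Reports to a counselor are not restricted to PTCM, so spontaneous eReferral reports are possible.
- The survey instruments and quitline scripts are not in the documents, so their content is unknown. The lack of an adverse event field in Table 3 is weak evidence: that table covers treatment engagement, and its PTCM column has no such field either.
- Part of any excess could be real, because planned NRT supply differs.

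It can also be said that Section IX may mean only medication handed out directly by the study. That would soften the contradiction, but eReferral participants would still be offered NRT through their assigned intervention, without the described monitoring.

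**Conclusion.** The point holds for non-serious events. As the plan is written, medication side effects are asked about at up to 7 scheduled contacts in PTCM. No scheduled question or quitline-to-PI route is described for eReferral, whose participants are offered 4 weeks of NRT. Any non-serious count by arm would be biased towards more events in PTCM and could not be separated from a real difference due to unequal supply. The statement in Section IX that only PTCM receives medication conflicts with Table 2 and the eReferral description in Section V; these passages must be reconciled.

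The size of the bias is not known. The range of about 2 to 9.5 rests on the assumed capture rates and on equal true rates in both arms, and should not be read as a forecast. The conclusion about eReferral rests on what the protocol describes; a side-effect item in the survey instruments would narrow it. The primary outcome is unaffected. This is a worthwhile low-cost improvement to safety reporting.

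**What to change.** 1. Reconcile Section IX with Table 2 and the eReferral description on which arms receive medication.
2. Add one identical medication side-effect item to the existing 1- and 3-month surveys in both arms, asked of anyone who used cessation medication since the last contact. Medication use is already measured there, so no new contact is needed.
3. Send positive answers from both arms to the same monthly PI review.
4. State that any by-arm statement on non-serious events uses this item only, and list automated-contact and coach reports separately as PTCM-only surveillance.
5. State that by-arm non-serious counts are not comparable for participants already past these surveys, who cannot be asked at the same time points.

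The cost is a short amendment, slightly longer surveys at two assessments and more reports for the PI to review.
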